This study is a randomized, placebo-controlled, single blind clinical trial. Seventy patients with ESRD on chronic HD and a functioning AVF will be recruited. Consent form will be obtained. History and physical, dialysis parameters and laboratory data (CBC, CMP, PTT & INR) will be obtained throughout the study. The following data will be documented on each patient: 1-Age/gender/race/body weight/cause of ESRD 2-Vintage of HD 3-Time since access was placed 4-Type and place of access and blood flow rate of access 5-History of prior access problems 6-Comorbid conditions (Hypertension, coronary artery disease, Diabetes Mellitus, Bleeding problems, peripheral vascular disease). 7-Current medications (Coumadin, Erythropoiesis stimulating agents, heparin, other antiplatelets, digoxin, statins). Patients will be randomized into two groups to receive: Group 1: Ticagrelor 90 mg PO BID Group 2: Placebo drug PO BID.

Subjects will have a screening visit and if they qualify for the study they will have 18 additional visits. All of these visits will occur while the subjects are at their normal dialysis treatment. Subjects will be randomized to either the Ticagrelor group or the placebo group. Subjects will be on study medication for 6 months then they will have a follow up period off drug for 6 months. Subjects will be seen twice a month while on study medication and once a month in the follow up period. While the subjects are on study medication we will assess any side effects of the study medication and put their relation to the study drug at each study visit. We will use clinical monitoring as suggested by Beathard (21). We will document the subject's adherence to the study, if they are hospitalized and what caused their hospitalization. A monthly intra-access flow will be obtained using ultrasound dilution by transonics as part of standard of care. Any change in the clinical assessment of the access, prolonged bleeding (>20 minutes) after removal of needles, trend of decreasing intra-access blood flow as determined by transonic (> 25% or original flow), or an access flow rate < 400 ml/min, will prompt a referral for a fistulogram. If confirmed stenosis (>50% stenosis of the access diameter) an intervention (angioplasty) will be performed. This intervention is part of the subject's standard of care.

Background

1. Provide the scientific background, rationale and relevance of this project.

The main renal replacement therapy for End stage renal disease (ESRD) in the USA is hemodialysis (HD). Vascular access for hemodialysis can be provided by means of an autogenous fistula, arteriovenous graft, or central venous catheter. The autologous brachio-cephalic (Brescia-Cimino) fistula remains the access of choice, since its patency and rate of infection are superior to those made of exogenous material once early failures are excluded (1). A functioning vascular access is crucial for HD. However, vascular-access failure (VAF) is common and is a major source of complications (1). Complications of the vascular access, particularly stenosis and thrombosis, continue to remain the Achilles' heel of HD therapy and lead to extensive morbidity in HD patients. VAF is the most common reason for hospitalization among HD patients (2-4). The economic burden of

IRB-HSR# 17224: Randomized, Placebo-controlled, Single Blind, Trial to Determine the Safety and Efficacy of Ticagrelor for Maintaining Patency of Arterio-Venous Fistulae Created for Hemodialysis

VAF is estimated at greater than 1 billion dollars per year (1) and continues to grow. Recent data have suggested a significantly high incidence of inflow stenosis of vascular access (14–42%) in this patient Population (5-7). Hence, guidelines were adopted for adequate monitoring and surveillance of the vascular access as well as criteria for adequate evaluation and timing intervention (8). Surveillance of an access is done by dynamic or static methods. Dynamic intra-access flow measures, by many methods as duplex doppler ultrasound, magnetic resonance angiography, and ultrasound dilution by transonics), are among the preferred methods of AV access surveillance (8). Patients with VAF are referred for evaluation and treatment if access flow rate <400-500 mL/min, in the presence of continuous persistent abnormalities in the surveillance parameters or a prospective trending drop of the access blood flow rate (8). There is no consensus in the literature as to the use of anticoagulants or antiplatelets for arterio venous fistula prophylaxis. . Multiple studies aiming at thromboprophylaxis to prevent VAF were done using various antiplatelet agents (Ticlopidine (9-12), Dipyridamole (11, 13, 14), Aspirin (15, 16) and Clopidogrel (17-19) showing variable results. While Sreedhara et al (13) showed that Dipyridamole can be thromboprophylactic for new arterio-venous graft (AVG), it failed to show any benefit to previously stenosed grafts. Dixon et al. (14) using extended release Dipyridamole in addition to aspirin, showed modest, though significant, decrease in AVG stenosis. Clopidogrel decreased thrombotic graft episode (18) but was reported to be associated with increased bleeding (17). Ticlopidine was used alone (9, 10, 21) or with Dipyridamole (11) to study its role in maintaining the patency of arterio-venous fistula (AVF) with controversial results.

Ticagrelor (Brilinta) is a new drug approved for use in patients with acute coronary syndrome to reduce the rate of thrombotic cardiovascular events. Early studies (please see investigator brochure for more information) showed that Ticagrelor achieves a higher inhibition of platelet aggregation as compared to Clopidogrel. The primary route of Ticagrelor elimination is via liver metabolism, thus, does not require dose adjustment in patients with renal impairments. Since Ticagrelor has not been used in hemodialysis patients for the purpose of preventing thrombosis in dialysis vascular accesses (Arterio-Venous Fistulae and Grafts), this study is designed as a pilot study to evaluate the feasibility and safety of Ticagrelor in hemodialysis patients with AVF vascular access to see if the treatment efficacy of Ticagrelor can preserve patency of hemodialysis vascular access better than Placebo.

Objectives: The primary objective is to evaluate the feasibility and safety of Ticagrelor in hemodialysis patients with AVF vascular access. The secondary objective is to evaluate the treatment efficacy in that whether Ticagrelor will preserve patency of hemodialysis vascular access better than Placebo. **Hypothesis:** Ticagrelor is safe and will preserve patency of hemodialysis vascular access (Arterio-Venous Fistulae) better than Placebo

The drug Ticagrelor, approved by FDA for patients with ACS, was never tested in patients with ESRD. In addition, if proven safe and effective in maintaining the patency of vascular access in patients with ESRD, which will be a new indication for the drug and hopefully will help, patients with ESRD maintain the patency of their access

Hypothesis to be Tested

Hypothesis: Ticagrelor is safe and will preserve patency of hemodialysis Arterio-Venous Fistulae better than Placebo. This is a Randomized, Placebo-controlled, Single Blind clinical trial. Seventy patients with ESRD on chronic HD and a functioning AVF will be recruited. Consent form will be obtained. History and physical, dialysis parameters and laboratory data will be obtained. Patients will be randomized into two groups to receive: Group 1: Ticagrelor 90 mg PO BID Group 2: Placebo drug PO BID Patients will be seen twice a month while on study treatment. We will assess any side effects and the relation to the study drug. -Clinical monitoring -Document adherence to the study -Document hospitalization with cause. -A monthly intra-access

IRB-HSR# 17224: Randomized, Placebo-controlled, Single Blind, Trial to Determine the Safety and Efficacy of Ticagrelor for Maintaining Patency of Arterio-Venous Fistulae Created for Hemodialysis

flow will be obtained using ultrasound dilution by transonics which is a standard of care procedure. Any change in the clinical assessment of the access, prolonged bleeding (>20 minutes) after removal of needles, trend of decreasing intra-access blood flow as determined by transonic (> 25% or original flow), or an access flow rate < 400 ml/min, will prompt a referral for a fistulogram. If confirmed stenosis (>50% stenosis of the access diameter) an intervention (angioplasty) will be performed. This intervention is part of the study patient's standard of care. Timeline of study: -6 Months recruitment phase -6 months active study phase: -6 months follow up: both groups will be monitored by complete physical examination, laboratory and dialysis data as well as monthly transonic assessment of intra-access blood flow rate will be done for standard of care and we will document if any intervention is required. -6 months statistical analysis and data documentation

Objectives: The primary objective is to evaluate the feasibility and safety of Ticagrelor in hemodialysis patients with AVF vascular access.

The secondary objective is to evaluate the treatment efficacy of Ticagrelor to see if it will preserve patency of hemodialysis vascular access better than Placebo.

Study Design: Biomedical

1. Will controls be used?

Yes

► IF YES, explain the kind of controls to be used.

Yes, we will have a group of study subjects that will be given a placebo in addition to what they would get that is the current standard of care for their medical issue.

2. What is the study design?

This is a randomized, placebo-controlled, single-blind study.

3. Does the study involve a placebo?

Yes

► IF YES, provide a justification for the use of a placebo

The placebo group can be used as an "add on" to standard of care in comparison to an investigational treatment added to standard of care. This is what will happen in this study.

Human Participants

Ages: 18 to 85

Sex: Male and Female

Race: All

Subjects- see below

1. Provide target # of subjects (at all sites) needed to complete protocol.

70

2. Describe expected rate of screen failure/ dropouts/withdrawals from all sites.

25%

3. How many subjects will be enrolled at all sites?

88

IRB-HSR# 17224: Randomized, Placebo-controlled, Single Blind, Trial to Determine the Safety and Efficacy of Ticagrelor for Maintaining Patency of Arterio-Venous Fistulae Created for Hemodialysis

4. How many subjects will sign a consent form under this UVa protocol?

88

5. Provide an estimated time line for the study.

We hope to have enrollment completed within 6 months of protocol approval.

Inclusion/Exclusion Criteria

1. List the criteria for inclusion

- Patients on chronic hemodialysis with a functioning arterio-venous fistula
- Subjects must agree to use adequate contraception to prevent pregnancy

2. List the criteria for exclusion

- Hemoglobin less than 9g/dL per chart review of the last Hemoglobin level obtained for standard of care.
- If the study subject can't be washed off of anti-coagulants or antiplatelets
- Recent history of bleeding over the last 3 months preceding enrollment
- History of bleeding disorder (hemophilia, Von Willebrandt disease, etc....). Anemia only if it is chronic and thrombocytopenia if the platelet count is consistently <125,000.
- Recent history of blood transfusion over the last 3 months preceding enrollment
- Recent serious injury or surgery over the last 3 months preceding enrollment
- History of gastro-intestinal ulcers
- Moderate-severe hepatic impairment (ALT/AST greater than 3-5 times the upper limit of normal).
- Uncontrolled blood pressure (SBP> 190 or DBP >110) pre or post dialysis
- History of stroke within the last 5 years.
- Pregnant females-self reported
- Hypersensitivity to Aspirin /antiplatelets
- Subjects using peroral anticoagulants
- History of intracranial hemorrhage
- Active pathological bleeding
- Hypersensitivity to ticagrelor or any component of the product

3. List any restrictions on use of other drugs or treatments.

Subjects using peroral anticoagulants will be excluded to avoid excessive bleeding risk. There will be a 4 day wash off for subjects who are taking anticoagulants and anti-platelets. If subjects can't be washed off of these medications then they cannot be included in the study.

Statistical Considerations

1. Is stratification/randomization involved?

Yes

► **IF YES, describe the stratification/ randomization scheme.**

Every other study subject will be on active study drug. Investigators and study personnel will be un-blinded.

IRB-HSR# 17224: Randomized, Placebo-controlled, Single Blind, Trial to Determine the Safety and Efficacy of Ticagrelor for Maintaining Patency of Arterio-Venous Fistulae Created for Hemodialysis

► IF YES, who will generate the randomization scheme?

UVa Statistician: [name]

2. What are the statistical considerations for the protocol?

Since Ticagrelor has not been used in hemodialysis patients for the purpose of preventing thrombosis in dialysis vascular accesses (Arterio-Venous Fistulae and Grafts), this study is designed as a pilot study in that patients are randomly assigned to receive Ticagrelor or placebo drug for a six-month treatment period plus an additional 6-month follow-up period. The primary objective is to evaluate the feasibility and safety of Ticagrelor in hemodialysis patients with AVF vascular access. The secondary objective is to evaluate the treatment efficacy in that whether Ticagrelor will preserve patency of hemodialysis vascular access better than Placebo. The study will follow intent-to-treat principle and all randomized patients will be included in the analyses for the primary and secondary objectives.

3. Provide a justification for the sample size used in this protocol.

Due to the pilot nature of this study, formal power analysis and sample size estimation is not essential. Nevertheless, we attempted to estimate the potential treatment efficacy in this study. We considered the outcome measure for efficacy evaluation is the time to first stenosis event during the study period. From our recent clinical data, it was estimated that approximately 36% of dialysis patients experienced stenosis event at one-year follow-up. We would expect that patients in the new drug arm would have 10% stenosis event rate at one-year follow-up, compared to the 36% stenosis event rate in the placebo group. With these considerations, the analysis of stenosis-free survival will require at least 21 events, which is the number of events needed for one-sided log-rank test at 5% significance level to have 80% power to show statistically significant difference when the true hazard ratio is 0.236. This estimation will result in that approximately seventy patients will be needed and evenly randomized into each study arm (35 patients in Ticagrelor and 35 in placebo). This is an open-label study. Upon completion of all the required screening assessments, eligible patients will be randomly assigned to the study drug or placebo at 1:1 ratio with a block size of 20 in accordance with the randomization schedule. The randomization schedule will be provided by the Department of Public Health, School of Medicine. Patients will be identified by unique subject identifier that will remain consistent for the duration of the study. The active study period is 6 months followed by 6 months of monitoring, and accrual rate is approximately 12 patients per month. To compensate for an estimated drop-out rate of 25%, we will recruit 88 patients to the study.

4. What is your plan for primary variable analysis?

We have recruited/consented a total of 54 subjects into this study. We have enrolled a total of 43 patients into the study, 23 in the Ticagrelor treatment arm and 20 in the placebo arm. We will evaluate the safety of Ticagrelor in hemodialysis patients with AVF vascular access by tabulating adverse events and severe adverse events for the two study arms, and the difference between the two arms will be tested by chi-square test.

5. What is your plan for secondary variable analysis?

For the secondary outcome, i.e., time to the first stenosis event, we will compare stenosis-free survival of Ticagrelor versus placebo using the Kaplan-Meier method. Survival probabilities and corresponding 95% confidence interval (CI) will be calculated at landmark time points for each arm, and survival difference between the two arms will be evaluated using a one-sided log-rank test stratified by the history of stenosis. Further, a stratified Cox proportional-hazards model will be used to derive the hazard ratio and 95% CI between the two regimens.

6. Have you been working with a statistician in designing this protocol?

Yes

IRB-HSR# 17224: Randomized, Placebo-controlled, Single Blind, Trial to Determine the Safety and Efficacy of Ticagrelor for Maintaining Patency of Arterio-Venous Fistulae Created for Hemodialysis

IF YES, what is their name?

[name]

Biomedical Research

1. What will be done in this protocol?

Subjects will be in this study for 1 year. Up to eighty eight patients with ESRD on chronic HD and a functioning AVF will be enrolled. For statistical purposes we will need to have seventy people complete the study. Consent form will be obtained. History and dialysis parameters will be taken at the screening visit. At the screening visit we will also be collecting a serum sample to perform a pregnancy test on female subjects of child bearing potential. This will be collected in a 3.5ml gold top serum separating tube. Study participants will be on the study medication (Ticagrelor) or placebo for six months (Visit 1 to Visit 12). Subjects will take the study medication twice a day. They will take it once in the morning and once in the evening. We will also instruct them to try and take it around the same times each day if possible. We will be collecting study medication to check for compliance at Visits 3, 6, 9, and 12. There will be a follow up for these subjects for six months (Visit 13 to Visit 18). Subjects will have a physical performed at screening, visit 12 (this is the last visit when subjects are on medicine), and at visit 18 which is the end of the study. We will be looking at hemoglobin levels that are collected as standard of care two times a month. We will be collecting the bleeding time weekly as well. This will be done at all visits (screening to Visit 18) which we define as the time it takes for a subjects' access to stop bleeding.

The following data will be documented on each subject at screening:

1-Age/gender/race/body weight/cause of ESRD

2-Vintage of HD

3-Time since access was placed

4-Type and place of access and blood flow rate of access

5-History of prior access problems

6-Comorbid conditions (Example: Hypertension, coronary artery disease, Diabetes Mellitus, Bleeding problems, peripheral vascular disease).

7-Current medications (Example: Coumadin, Erythropoiesis stimulating agents, heparin, other antiplatelets, digoxin, statins)

This data will be obtained from the dialysis computer system and will be verified with the subject.

8-Physical Exam

9-Vital signs (blood pressure, heart rate, and weight) will be obtained from the subject's dialysis record.

Adverse events and concomitant medications will be reviewed at each study visit. We will also note any access issues at each study visit.

Study Medication Stopping Rules for Prolonged Bleeding:

If post treatment bleeding time is prolonged more than 30 minutes we will stop the study drug and refer for fistulogram,

If bleeding still persists after fistulogram and intervention we will continue to hold the study drug and do work up for bleeding. We will continue to hold study drug for 5 days if signs of increased tendency for bleeding as recurrent Epistaxis > twice in one week, if any evidence of GI bleed, or if Hgb should drop > 1gm in one week. If the bleeding is believed to be drug related or it no resolution occurs the subject will be withdrawn from the study.

We will also hold study drug for 5 days if hemoglobin is consistently less than 8g/dL for 2 consecutive weeks, or hemoglobin dropping 1g/dL in one week.

IRB-HSR# 17224: Randomized, Placebo-controlled, Single Blind, Trial to Determine the Safety and Efficacy of Ticagrelor for Maintaining Patency of Arterio-Venous Fistulae Created for Hemodialysis

For a prolonged bleeding event standard practice will be applied, including: (prolonged bleeding is defined as bleeding more than 30 minutes)

- **Direct pressure.** Any bleeding that warrants an emergency department visit should be immediately controlled with the application of direct digital pressure to the puncture site for 5-10 minutes. Once the bleeding abates, the patient should be observed for rebleeding or early thrombosis for 1-2 hours.
- **Gelatin sponges.** Commonly seen in the emergency department as Gelfoam®, this adjunct may aid in the hemostasis of bleeding AV grafts. Although studies or case reports of this material being used in this setting are not found in the medical literature, our clinical practice has demonstrated success by including it in the management of this problem.

Life-Threatening Bleeding From Hemo Access

A vascular surgeon should be emergently consulted if hemorrhage cannot be quickly controlled. An adjunctive suture may be placed if there appears to be a small laceration of the graft rather than a puncture wound. This suture is used only after other measures to control bleeding described above have also failed.

Other life threatening bleeding: Subjects will be sent to the emergency department

2. Will you be using data/specimens in this study that were collected previously, with the use of a research consent form, from another research study?

No

3. List the procedures, in bullet form, that will be done for research as stipulated in this protocol.

- Physical Exams
- Administration of Investigational Drug
- HcG Blood Pregnancy Test
- Collection of Bleeding Time

Note: Laboratory data will be captured and recorded for research purposes from blood collected as part of the subject's clinical care-no additional blood is collected for the purpose of this study.

4. Will any of the procedures listed in item # 2 have the potential to identify an incidental finding?

Yes

► IF YES, check one of the following two options:

X The examination(s) utilize(s) the same techniques, equipment, etc., that would be used if the subject were to have the examination(s) performed for clinical care. There exists the potential for the discovery of clinically significant incidental findings.

- The PI takes full responsibility for the identification of incidental findings:
- The PI will inform the subjects verbally of all incidental findings that are of clinical significance or are of questionable significance.
- A follow-up letter describing the finding should be provided to the subject with instructions to either show the letter to their PC or if the subject has no PCP, the subject should be instructed to make an appointment at UVa or at the Free Clinic.

IRB-HSR# 17224: Randomized, Placebo-controlled, Single Blind, Trial to Determine the Safety and Efficacy of Ticagrelor for Maintaining Patency of Arterio-Venous Fistulae Created for Hemodialysis

5. Do any of the procedures listed above, under question # 2, utilize any imaging procedures (e.g. ultrasound, CT scans/ x-rays etc.)? If yes, LIST PROCEDURES: No

6. Will you be using viable embryos? No

7. Will you be using embryonic stem cells? No

Specimens

Specimen Information

1. Describe the type of specimen to be used:

Answer/Response: At the screening visit only, we will collect a 3.5ml gold top serum separating tube from women in the study who are of child bearing potential.

2. Will the specimen be obtained BEFORE a subject has signed a consent form?

IF YES, or if consent or documentation of consent is waived and the specimen is identifiable per HIPAA regulations, the research team will be required to track this disclosure with Health Information Services.

Answer/Response: No

3. Will you be using discarded specimens?

Answer/Response: No

Answer the following two questions as it pertains to ALL blood being drawn for this study.

► IF NO, and taking a blood sample, will blood be taken more than 2 times/week?

Answer/Response: No

► IF NO, and taking a blood sample, check the option(s) below which match the subject population.

healthy, non-pregnant adults who weigh at least 110 pounds.

Amount will NOT exceed 550 cc in an 8 week period

Amount to exceed 550 cc in an 8 week period

Non- healthy or pregnant adults and/or children

Amount will NOT exceed the lesser of 50ml or 3 ml/kg in an 8 week period

Amount will exceed the lesser of 50 ml or 3 ml/kg in an 8 week period

Specimen Labeling

1. What information/ HIPAA identifiers will be on the specimen label when it is given to the study team (from clinical labs or other source outside the study team) and/or what information will you put on the specimen?

Example: name, date of collection, subject # medical record#

Answer/Response: Name, Date/Time of Collection, Subject MRN#

2. If the specimen is given to the study team with information on the label will you delete any of the information on the specimen label?

Answer/Response: No

3. Will any additional data be linked to the specimen by way of a code?

Example: name, date of collection, subject # medical record# , diagnosis, clinical information

Answer/Response: No

IRB-HSR# 17224: Randomized, Placebo-controlled, Single Blind, Trial to Determine the Safety and Efficacy of Ticagrelor for Maintaining Patency of Arterio-Venous Fistulae Created for Hemodialysis

4. Will the analysis on the specimen be done soon (within 24 hours) after it is collected?

INSTRUCTIONS: This question does not refer to a specimen that is collected for long term tissue banking, but rather analysis that is already described in the protocol.

Answer/Response: Yes

Specimen Shipping

1. Do you plan to ship any specimens outside of UVA?

Answer/Response: No

Data and Safety Monitoring Plan

*If you have any questions completing this section call [name], [name] or [name] for assistance
A Sponsor is defined as entity that will receive data prior to publication.*

1. Definition:

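### Access blood flow is recorded at screening and obtained monthly but enters no analysis, leaving efficacy to about 8 to 9.5 expected stenosis events where the plan asks for 21

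*Combined protocol and SAP*

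**What the plan says.** **Measurement.** Biomedical Research item 1 opens its data list with "The following data will be documented on each subject at screening", and the list includes "4-Type and place of access and blood flow rate of access". On later readings the opening study summary says: "A monthly intra-access flow will be obtained using ultrasound dilution by transonics as part of standard of care". For the six months off drug, Hypothesis to be Tested says "monthly transonic assessment of intra-access blood flow rate will be done for standard of care and we will document if any intervention is required".

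**Use.** Flow has a clinical role only. A fall of more than 25%, or "an access flow rate < 400 ml/min, will prompt a referral for a fistulogram". Two triggers that are not flow readings lead to the same referral: a change in the clinical assessment of the access, and prolonged bleeding after needle removal.

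**Analysis.** Under Statistical Considerations, item 4 tabulates adverse events, and "the difference between the two arms will be tested by chi-square test". Item 5 covers efficacy: "For the secondary outcome, i.e., time to the first stenosis event, we will compare stenosis-free survival of Ticagrelor versus placebo using the Kaplan-Meier method". It adds a one-sided log-rank test and a Cox model, both stratified by history of stenosis. Neither item mentions flow.

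**Size.** Item 3 asks for at least 21 events, from a "one-sided log-rank test at 5% significance level to have 80% power to show statistically significant difference when the true hazard ratio is 0.236". Item 4 reports 43 enrolled, 23 on ticagrelor and 20 on placebo.

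**The concern.** The secondary objective is whether ticagrelor preserves patency, and flow is the measurement the protocol itself uses to watch patency. Each subject should have a screening value and up to 12 monthly readings, yet the planned efficacy analysis uses only whether and when a first stenosis was found.

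Three things are at stake. With so few events, the hazard ratio will be imprecise. It is also open to chance imbalance in screening flow, a plausible prognostic factor that is recorded but not adjusted for. And the event depends partly on referral decisions by staff who are un-blinded (Statistical Considerations item 1). A machine reading is less exposed to that, and every subject with readings contributes to its analysis.

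**Working it through.** **1. The plan's own figures.** HR = ln(0.90)/ln(0.64) = 0.236, as stated. Freedman events = (z_α + z_β)² × [(1 + HR)/(1 − HR)]². Two-sided 5% with 80% power gives 20.5, so 21 events. One-sided 5%, as worded, gives 16.2, so 17. The stated 21 thus matches the two-sided calculation, which is a separate matter. The planned 70 subjects would yield 35 × 0.10 + 35 × 0.36 = 16.1 events at the design rates.

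**2. Expected events in the 43 enrolled.**
- Design rates: 23 × 0.10 + 20 × 0.36 = 9.5.
- With 25% dropout, exponential over the year, the expected proportion per arm is λ/(λ + μ) × (1 − e^−(λ+μ)), where μ = −ln 0.75. This gives 23 × 0.0871 + 20 × 0.3162 = 8.3.
- No drug effect (36% in both arms): 43 × 0.36 = 15.5, or 43 × 0.3162 = 13.6 with dropout.
- HR 0.5: 23 × 0.20 + 20 × 0.36 = 11.8.

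**3. Power of the planned event test (one-sided 5%).** Schoenfeld: Φ(√(E × 23/43 × 20/43) × |ln HR| − 1.645). Freedman: Φ(√E × (1 − HR)/(1 + HR) − 1.645).

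| Events | HR | Schoenfeld | Freedman |
|---|---|---|---|
| 8 | 0.236 | 65% | 54% |
| 9.5 | 0.236 | 72% | 60% |
| 12 | 0.5 | 33% | – |

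A simulated unstratified log-rank test gives 68% at HR 0.236 (63% with dropout) and 34% at HR 0.5 (31% with dropout).

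**4. Screening flow as a Cox covariate.** Simulation of 23 v 20 subjects, marginal rates 10% v 36%, 2,500 runs per case, assumed log HR per SD of log flow from −0.4 to −1.0. Power, unadjusted then adjusted:
- No dropout: 66/68, 70/72, 67/75.
- 25% dropout: 63/63, 63/65, 67/72.

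The gain is 0 to 8 points, and four of the six cases gain 0 to 2. The Monte Carlo standard error of each power is about √(0.67 × 0.33/2500) = 0.9 points. Size was about 5 to 6%.

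**5. Flow as an outcome.** The documents give no SD or correlation for flow, so these are assumptions: correlation 0.8 between monthly readings, and correlation r with baseline from 0.5 to 0.8. For the mean of six on-drug readings adjusted for baseline (two-sided 5%, 80% power):

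detectable difference = 2.80 × √[(1 + 5 × 0.8)/6 − r²] × √(1/n₁ + 1/n₂)

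| r | 23 v 20 | 17 v 15 (25% loss) |
|---|---|---|
| 0.5 | 0.65 SD | 0.76 SD |
| 0.7 | 0.50 SD | 0.58 SD |
| 0.8 | 0.38 SD | 0.44 SD |

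As a percentage, with an assumed CV of 30% to 50%: 1 − exp(−d × √ln(1 + CV²)). At r = 0.7 this is 14% to 21%, or 16% to 24% with loss. At r = 0.5 and CV 50% it is 27%, or 30% with loss.

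**6. Dilution.** Suppose flow falls only in subjects who stenose. At constant hazards the arms differ in cumulative stenosis by 0.9^(t/12) − 0.64^(t/12). Over months 1 to 6 this is 2.8, 5.4, 8.0, 10.4, 12.7 and 14.9 points, mean 9.0. If each event brings an assumed lasting fall of 25% to 50% in flow, the mean log difference is 0.090 × 0.288 = 0.026 to 0.090 × 0.693 = 0.062, a difference of about 3% to 6%. If the fall begins 2 to 6 months before the event, it is about 3% to 10%. At r = 0.7 and CV 30% to 50%, power is then about 6% to 54%.

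**The case against.** The strongest reply is that this is a pilot with feasibility and safety primary, and that preferring a clinical event to a surrogate is a legitimate choice. That stands, and it limits flow to a supportive role. Several stronger readings must also be set aside:

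- A reader might infer that a flow analysis has more power than the event test. Step 6 shows that this holds only if the drug shifts flow broadly in most subjects, which the documents do not say. SD units and hazard ratios are not directly comparable either.
- A reader might infer that the detectable difference is reassuringly below the protocol's 25% trigger. That trigger is a fall within one patient; the detectable figure is a difference between arm means, and it reaches 27% to 30% in the unfavourable cases.
- A reader might take the monthly values as already in the trial data. They are obtained as standard of care. For follow-up, the text commits only to documenting interventions, and the data-capture note in Biomedical Research item 3 covers laboratory data.
- A reader might think that stopping at first intervention is harmless because referral follows observed flow. Clinical signs and bleeding also prompt referral, and bleeding is a listed ticagrelor effect, so truncation may differ by arm for reasons that flow does not explain. Truncation and worst-rank scoring also bring the un-blinded referral decision back in.
- An outcome added after 43 enrolments, with un-blinded staff, could be informed by the data.

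These points reduce what a flow analysis can claim. They do not explain why flow is left out altogether.

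**Conclusion.** The omission is real. Flow is recorded at screening and obtained monthly, and no stated analysis uses it as an outcome or covariate. The only efficacy analysis can expect about 8 to 9.5 events at the design rates, or 14 to 16 with no drug effect, against 21 required. Power at the plan's very large effect is roughly 54% to 72%, and about a third at HR 0.5. These event counts rest on the plan's own rates and enrolment.

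The benefit of using flow is modest and uncertain. The covariate adds 0 to 8 points of power, according to an assumed prognostic strength. The repeated-measures analysis could detect about 0.38 to 0.65 SD (0.44 to 0.76 SD with 25% loss), under correlations that the documents do not give. Its case is that it adds an estimate from a less judgement-dependent measurement, not that it would replace or outperform the event analysis. The planned analysis is not invalid without it.

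**What to change.** In Statistical Considerations item 5 add:

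1. **Covariate.** Fit the Cox model stratified by history of stenosis with log screening access flow as a covariate, and report it alongside the planned analysis.
2. **Supportive flow analysis.** Fit a repeated-measures model to log monthly access flow for months 1 to 6, with months 7 to 12 modelled separately. Include arm, month, arm by month, log baseline flow and history of stenosis. Label it exploratory and report an estimate with 95% confidence interval. Use readings up to the first access intervention.
3. **Sensitivity analyses.** Repeat with all readings, and with intervened subjects ranked worst. Give the reason: referral also follows clinical signs and prolonged bleeding, which may differ by arm.
4. **Data and disclosure.** Record each monthly value on the case report form, and state that the flow analysis was added after enrolment with un-blinded staff.

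The cost is some wording, transcription of values from dialysis records and a little analysis. Some standard-of-care months will be missing. No visit, test or referral rule changes.
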